Social and Behavioral Intervention to increase solid organ and tissue donation

Clinical Trials Number: NCT02318849

[figure not shown]
Unique protocol number: R39OT26993 from the Health Resources and Services Administration

Document date: May 27, 2023

Study Design/Intervention Protocols and Statistical Analyses Protocols

The eHealth study used a cross-sectional design that included a sequential, multiple baseline survey design that was introduced over two years at the three Hawaii university campuses. For example, undergraduate students at one site (University of Hawaii at Manoa-UHM) participated in three semesters of the DOD intervention and students at two sites (University of Hawaii at Hilo-UHH), Hawaii Pacific University-HPU) received two sequential semesters. **Figure 1** shows the study design with pre/post surveys and a sequential introduction of the intervention across three years (four semesters).

Figure 1. Study Design

Thus, either a baseline or post-test survey was administered at the start and/or the end of a semester depending on when the online intervention was introduced at a site. All students at the site were recruited to take the surveys regardless of whether or not they had completed a survey at any point in the past. Therefore, some survey analyses included cross-sectional samples and some analyses included a cohort sample of students. Data collection protocols for online surveys from undergraduate students were approved by the University of Hawaii's Human Studies Program in October 2014 (CHS 22372) with Hawaii Pacific University's Institutional Review Board ceding to the University of Hawaii's IRB.

Survey questions for primary outcomes:

[figure not shown]
- 1. Status as a designated organ donor on Department of Motor Vehicles (DMV) issued driver's license, state-issued ID card or donor registry.
- 2. Reported discussion about their choice to be (or not be) an organ donor on their DMV issued driver's license with their parents or other family members.

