Protocol for Sample Size / **Power calculations for surveys:** Simulations were run to determine the achieved power of our multiple baseline design resulting in an average of 240 participants per site for surveys collected at the beginning and end of four academic semesters at UHM and UHH and five academic semesters for HPU (20 data points, total n = 4,800). We assigned 60% of the students at baseline to already be a DOD (prior to being exposed to the intervention), based on the proportion we observed in previous work. Using an α =0.05 (two-sided) and a power of 80%, a simulation of 500 iterations found that the minimum detectable difference (MDD) in DOD prevalences comparing the 9 pre- and 11 post- intervention assessments, using our analysis approach, was 4 percentage points for an average change overall (3 campuses) and was 7 percentage points within a single campus; this was true assuming no change or a 3 percentage point drift in the pre-intervention prevalences over time.

Protocol for recruiting students for Study Surveys and Intervention activities Before taking the iDecide survey, students had to confirm they had read the consent form and actively consent (click yes). Eligibility was the verified. Only undergraduates enrolled at the three participating universities (UHM, UHH, HPU) were eligible, with enrollment verified by the respective university. Age was the only other eligibility criteria (18 years or older). Of the 8,001 online

consent forms completed, 853 (10.7%) reported enrollment at a nonparticipating university, and 2,073 (25.9%) didn't finish the survey. After verifying enrollment status for the remaining 5,075 survey entries, 248 (4.9%) were excluded because the student was not currently enrolled or was a graduate student, or their survey was a duplicate within that assessment; 4,837 was the final count.

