I'll do it if YOU do it first! Be an advocate, tell someone you know THEY can save 8 lives and improve the quality for up to 20 more, just by being an organ donor. Spread the word!	Sp2016	Sp2016	

4) Statistical Analyses Protocols

Two types of data sets would be created: a cross-sectional set and a longitudinal set. The cross-sectional dataset would include data from all surveys at each of the 20 assessment points (see Figure 1). The design allowed for students

to complete surveys at more than one assessment point. Due to uniqueness of student email addresses, those with repeat surveys could be identified. Thus, students could complete one or more pre-intervention surveys, one or more post-intervention surveys, or complete both pre and post-intervention surveys. The longitudinal dataset would include only those students who completed one or more baseline surveys and one or more post-test surveys.

The primary hypothesis was that exposure to the intervention would increase the percentage of students who reported being DODs on license and/or who spoke to their parents about their choice to be (or not be) a DOD on their license, and exposure would also improve knowledge and attitudes about OD. The primary analysis of the cross-sectional data used a logistic model of the outcomes DOD status or "talk to parents" regressed on a set of indicator variables reflecting each of the 20 assessment points (time by school combinations), adjusted for student's age, sex, race, and religion. Predicted DOD status (or family talk status) was computed from the model for each assessment point and the predicted statuses were compared between pre-intervention and post-intervention assessments using a t-test to test the primary hypothesis. We also repeated the test within subgroups defined by school and by covariates, such as race, to determine if the intervention effect differed by subgroups. Linear models regressing knowledge and attitude scores on assessment indicator variables and adjustment factors were used to determine the intervention effect on these scores.

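### Two primary outcomes share one primary hypothesis, with no success rule and no multiplicity control

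*Combined protocol and SAP*

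**What the plan says.** The opening design section of the combined protocol and SAP has a list headed "Survey questions for primary outcomes". It contains two items. The first is status as a designated organ donor. The second begins "Reported discussion about their choice to be (or not be) an organ donor on their DMV issued driver's license" and refers to talks with parents or other family.

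Section 4, *Statistical Analyses Protocols*, states one primary hypothesis covering both: exposure would "increase the percentage of students who reported being DODs on license and/or who spoke to their parents about their choice". The same sentence adds that knowledge and attitudes would also improve. A logistic model is fitted for each of the two outcomes. "Predicted DOD status (or family talk status) was computed from the model for each assessment point", and these predictions are "compared between pre-intervention and post-intervention assessments using a t-test to test the primary hypothesis". The section gives no significance level, order of testing, requirement that both outcomes succeed, or adjustment.

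The one significance level in the document is in the sample size section: "Using an α =0.05 (two-sided) and a power of 80" per cent. It belongs to a simulation of "the minimum detectable difference (MDD) in DOD prevalences". No detectable difference is given for family discussion.

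**The concern.** Two separate tests feed one primary claim. If a significant result on either outcome is enough, and each is judged at 0.05, chance has two opportunities to produce a positive primary finding. The error rate for the claim as a whole is then above the 5% used in the power section. A reader of the results could not tell whether success on one outcome and failure on the other confirms or refutes the hypothesis, because the plan sets no rule in advance. The second primary outcome would also carry a confirmatory claim without a power statement of its own.

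**Working it through.** **Inputs from the document.** Two primary outcomes (list of survey questions). Two-sided alpha 0.05, power 80%, an average of 240 surveys per assessment point, 20 points, 9 before and 11 after the intervention, and a baseline of 60% (sample size section: "We assigned 60% of the students at baseline to already be a DOD"). Hence 9 × 240 = 2,160 surveys before and 11 × 240 = 2,640 after, 4,800 in total.

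**Assumptions.** Surveys are independent, with no allowance for repeat respondents or covariates. The correlation between the two test statistics is not given, so a range is shown.

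**Step 1: reproduce the plan's figure.** With baseline variance in both periods, the standard error is √[0.6 × 0.4 × (1/2,160 + 1/2,640)] = 0.01421. The detectable difference at 80% power is (1.960 + 0.842) × 0.01421 = 3.98 points. With the variance taken at the alternative it is 3.94. Either agrees with the stated 4 points.

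For 60% against 64%, the pooled proportion is (2,160 × 0.60 + 2,640 × 0.64)/4,800 = 0.622. The null standard error is 0.01407 and the standard error under the alternative is 0.01408. Power is Φ[(0.04 − 1.960 × 0.01407)/0.01408] = 81.1%.

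**Step 2: error for two unadjusted tests.** If the tests are independent, the chance of at least one false positive is 1 − 0.95² = 9.75%. The upper bound under any dependence is 0.05 + 0.05 = 10%. For a false increase only, each test contributes 0.025, so the rate is 1 − 0.975² = 4.94%. With bivariate normal test statistics:

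| Assumed correlation | At least one false positive, either direction | Ratio to 5% | At least one false increase (2.5% for one test) |
|---|---|---|---|
| 0 | 9.75% | 1.95 | 4.94% |
| 0.2 | 9.64% | 1.93 | 4.84% |
| 0.5 | 9.07% | 1.81 | 4.54% |
| 0.8 | 7.81% | 1.56 | 3.90% |
| 0.9 | 7.04% | 1.41 | 3.52% |

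**Step 3: effect of Holm.** The smaller p-value is compared with 0.025. If it passes, the other is compared with 0.05. When neither outcome has an effect, the chance of any false positive is 1 − 0.975² = 4.94% for independent tests, and at most 5% under any dependence.

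The worst case for donor status is that it must pass 0.025. The detectable difference is then (2.241 + 0.842) × 0.01421 = 4.38 points (4.33 with the variance at the alternative). Power for 4 points is Φ[(0.04 − 2.241 × 0.01407)/0.01408] = 72.6%.

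**The case against.** Several parts of the opposing case stand and limit how the point may be put.

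- **The level is inferred.** Section 4 states no alpha. The 0.05 is tied to a simulation of donor prevalence. It is the only level in the document and nothing reduces it, but the family-discussion test has no stated level at all.
- **The conjunction may describe students.** In the hypothesis sentence, *and/or* sits inside the clause about students. A reader might infer an explicit rule that either outcome wins. The document does not state one. Nor does it define a composite outcome or require both outcomes to succeed, and requiring both would remove the inflation. On either reading there are two primary tests and no rule for combining them.
- **The hypothesis is directional.** The 9.75% includes false decreases, which could not support it. The matching comparison is 4.94% against 2.5%.
- **Independence is the high end.** Both outcomes come from the same students in the same survey. A reader might infer that the error is simply doubled. That is close at low to moderate correlation, but the ratio falls to about 1.6 at 0.8 and 1.4 at 0.9.

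A reader might also count knowledge and attitude scores as two further chances to win, which for four independent tests would give 1 − 0.95⁴ = 18.5%. The document does not support this. Those scores are joined to the hypothesis as something that would also improve, they are absent from the list of primary outcomes, and they have their own linear models.

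Finally, recruitment ended in December 2016, the document is dated May 2023, and section 4 already reports a propensity model fitted to 2,129 surveys. No sentence added now can count as pre-specified. This rules out a fixed testing order, since an order chosen now would not protect the error rate. It does not rule out Holm, which involves no choice of order.

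**Conclusion.** The point holds in a conditional form. The plan has two primary outcomes under one hypothesis, tests each separately, and gives neither a success rule nor multiplicity control. If each test is run at the only level in the document and either can support the hypothesis, the chance of at least one false-positive primary test is up to 9.75%. It is about 9.1% at an assumed correlation of 0.5 and 7.8% at 0.8. For false claims of an increase alone, the rate is up to 4.94% where one test would give 2.5%. The inflation is present at every correlation examined, but its exact size is unknown because the document gives no correlation.

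**What to change.** Apply Holm to the two primary p-values, donor status and family discussion, at overall two-sided 0.05, and confine any primary claim to the outcome or outcomes that pass. State openly that the adjustment was added after data collection. Describe knowledge and attitude scores as secondary, in line with the list of primary outcomes.

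The work is one sentence in the analysis section and a calculation on two p-values that the plan already produces. The price is sensitivity. At worst the detectable difference for donor status rises by about 0.4 points, from 4.0 to 4.4, and power for a 4-point difference drops from about 81% to 73%, treating surveys as independent. If family discussion has the smaller p-value and passes 0.025, donor status is tested at the full 0.05 and loses nothing. With data collection complete, this loss cannot be recovered by a larger sample and should be acknowledged when the results are reported.

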The primary analysis models were repeated in the longitudinal sample, accounting for repeated measures. Further, a logistic model of post-intervention DOD status was performed among the longitudinal sample where the students never reported being a DOD at any pre-intervention assessment. All post repeated measures for these individuals were included in one model (allowing for repeated yes answers) and all post repeated measures up until when the first yes reported for DOD was included in a second model. The independent variables included the assessment indicators, age, sex, ethnicity and religion. The predicted percentage adopting DOD would be obtained from the model and tested against 0 using a t-test. This comparison was repeated for each post-intervention time (e.g., 1st post-test) and for each school, as well as by subgroups defined by covariates. A similar analysis was performed for the "talk to parents" outcome in the subset who never reported having this conversation on any pre-intervention survey.

Lastly, in order to determine if the intervention was more effective in students less likely to be a donor, protocols stratified the statistical analyses using a "propensity score" based on static student characteristics. We anticipated that students with characteristics making them less likely to become a DOD might be more influenced by our intervention. Propensity scores were developed for DOD status by using a logistic regression of DOD status using pre-intervention data to determine predictors from among demographic/sociocultural variables (e.g., age, sex, race, religion, place of birth, years lived in HI, college year, tuition source, college major, college credits, recruitment method, study site and time). The resulting DOD model based on 2129 surveys (Donor: Yes=1137, No=992) included significant factors of age, sex, race, college year, religion, and tuition source, using stepwise variable selection. The resulting logistic regression equation would then be applied to all surveys to obtain predicted probabilities that were used as "propensity scores." The primary analyses for the cross-sectional data set was performed separately for surveys with a low propensity score < 50% and for surveys with a high propensity score ≥ 50%. The analyses for the longitudinal data set were also stratified by low and high pre-intervention propensity scores, based on the average for students who provided ≥ 1 pre-test survey.

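### The primary model omits college year and tuition source, two factors the plan's own model kept as predictors of donor status: a risk of avoidable residual confounding

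*Combined protocol and SAP*

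**What the plan says.** The opening design section describes an unrandomised study: "The eHealth study used a cross-sectional design that included a sequential, multiple baseline survey design". All students at a site were invited to each survey, whether or not they had answered before.

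Under 4) Statistical Analyses Protocols, the primary cross-sectional analysis is a logistic model of each primary outcome, "regressed on a set of indicator variables reflecting each of the 20 assessment points (time by school combinations"), and "adjusted for student's age, sex, race, and religion". For the test itself, "the predicted statuses were compared between pre-intervention and post-intervention assessments using a t-test to test the primary hypothesis". The same models are repeated in the longitudinal sample. The model for new donors among students who were never donors before the intervention again lists only age, sex, ethnicity and religion beside the assessment indicators.

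The last paragraph of that section builds a score for donor status from pre-intervention data. The fitted model "included significant factors of age, sex, race, college year, religion, and tuition source, using stepwise variable selection". Its basis is given as "The resulting DOD model based on 2129 surveys (Donor: Yes=1137, No=992"). The score is then used to stratify: "The primary analyses for the cross-sectional data set was performed separately for surveys with a low propensity score < 50"%, and likewise for scores at or above that cut. The stated purpose is to see whether the intervention works better in students less likely to be donors.

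**The concern.** The plan holds evidence, from its own data, that six factors predict donor status, and it adjusts the primary comparison for four of them. No reason is given for leaving out the other two.

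This matters because nothing in the design balances the pre- and post-intervention respondents. They were volunteers reached through faculty emails, student organisations, class presentations and extra-credit sites. At each site the pre-intervention surveys come before the post-intervention ones. A student who answers again in a later academic year will usually have moved up a class. The campuses also had different numbers of intervention semesters (three at one, two at the others), and no weighting by campus is described for the t-test. If tuition source or college year differs by campus, that difference can enter the contrast. A change in either factor between pre and post could therefore be read as an intervention effect, or could hide one.

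**Working it through.** **1. Which covariates are where** (both from 4) Statistical Analyses Protocols)

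| Factor | Donor-status model, pre-intervention | Primary model |
|---|---|---|
| Age | kept | adjusted |
| Sex | kept | adjusted |
| Race | kept | adjusted |
| Religion | kept | adjusted |
| College year | kept | absent |
| Tuition source | kept | absent |

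The donor-status model rests on 1,137 + 992 = 2,129 surveys, of which 1,137 / 2,129 = 53.4% were from donors. College year and tuition source were kept in a model that also contained the other four, so the plan's evidence is that they add to the four.

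**2. The plan's yardstick** (inputs from the sample size section)

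- 240 surveys per assessment; 9 pre and 11 post: 9 × 240 = 2,160 and 11 × 240 = 2,640, total 4,800.
- Baseline prevalence 60%, two-sided alpha 0.05, power 80%, stated minimum detectable difference (MDD) 4 points overall.
- A two-proportion calculation, 60% versus 64%, gives power 0.811, and 80% power is reached at 3.95 points. The stated 4 points is reproduced.
- A simulated unadjusted t-test on 9 versus 11 assessment proportions gives power 0.765 at 4 points, somewhat lower. The 4-point figure is a fair yardstick either way.

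**3. Size of a possible bias**

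For one omitted two-level factor, bias is approximately

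bias = (gap in donor prevalence between levels, given the four covariates) × (pre-to-post shift in the share at one level).

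The documents give neither term: no coefficients for the two factors and no pre/post distributions. The gaps and shifts below are assumptions. For the effect on the test:

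- SE = √[0.60 × 0.40 × (1/2,160 + 1/2,640)] = 1.42 points
- Type I error = Φ(−1.96 − bias/SE) + 1 − Φ(1.96 − bias/SE)

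| Assumed gap (points) | Assumed shift (points) | Bias (points) | Share of 4-point MDD | Two-sided type I error |
|---|---|---|---|---|
| any | 0 | 0 | 0% | 0.050 |
| 5 | 5 | 0.25 | 6% | 0.054 |
| 10 | 10 | 1.0 | 25% | 0.108 |
| 10 | 20 | 2.0 | 50% | 0.291 |
| 20 | 20 | 4.0 | 100% | 0.804 |

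The SE treats surveys as independent and ignores covariates, so the last column is a guide only. The bias can have either sign.

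**The case against.** The strongest objection is that predicting the outcome is only half of what makes a confounder. College year or tuition source must also differ between pre and post surveys, given the four covariates, and the documents do not say that they do. This stands. A reader might infer that the primary result is confounded, or that a bias of some definite size has been found. The documents support neither.

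A reader might also infer that covariate adjustment is the only protection in the plan, or that the two factors are ignored altogether. Neither is so. The staggered introduction across campuses, the repeat of the primary models in students with both pre and post surveys, and the analysis of students who were never donors beforehand all give some protection. The two factors also enter the score that stratifies the primary analysis. These safeguards are partial, however. The longitudinal models are described with the same limited covariates. The strata use a single cut at 50%, are meant to detect effect modification, and mention no added covariates within strata.

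Age may be thought to stand in for college year. It probably overlaps, but college year was kept in a model that already contained age.

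Two further points stand. Stepwise selection can overstate predictors, and here it used pre-intervention data that are part of the primary comparison. The model also concerns donor status only, so it says nothing about the family-discussion outcome.

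Finally, college year advances with time, so in the longitudinal sample it is entangled with the pre/post contrast. The same is true of age, which the plan already adjusts for. This limits how the longitudinal fix should be made and does not touch the cross-sectional one.

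**Conclusion.** The omission is established from the text: two collected factors, kept by the plan's own model as predictors of donor status beyond the four adjusted ones, are missing from the primary model without explanation. What follows is a risk of avoidable residual confounding, not a demonstrated bias. Its size is unknown. It is zero without a shift in mix and 0.25 to 4 points over the assumed grid, or 6% to 100% of the 4-point MDD. The upper end needs both a 20-point gap and a 20-point shift, and nothing in the documents points to values that large.

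The point is firm for donor status and weaker for family discussion. Adjustment for these two factors would not remove confounding with calendar time. The change is still worth making because it is specific, uses data in hand, and carries little danger of over-adjustment: the contests could hardly have altered a student's class standing or tuition source.

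**What to change.** - Tabulate college year and tuition source for pre- and post-intervention surveys. This shows directly whether the risk is real.
- Add both to the adjustment set of the cross-sectional donor-status model, and report the six- and four-covariate results side by side.
- Data collection ended in December 2016 and the document is dated May 2023. If results are already known, label the six-covariate model as added later, so that it does not quietly replace the stated one.
- Do the same for family discussion for consistency, noting that the selection model did not address that outcome.
- In the longitudinal models, use college year at the student's first survey, because it advances with time.
- State why the two factors were left out of the stated primary model.

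The cost is a few extra parameters against about 4,800 surveys and no new data collection. The drawback is a covariate set informed by stepwise selection on the study's own pre-intervention data, which is why both results should be shown.

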Protocols included total of 15 to 22 contests per site per semester were held during the intervention, with the largest number of contests (n=58) being held in the Spring of 2016 when all three sites were active in the intervention (see Figure 1). As an indicator of the dose for our gamification protocol, up to seven Instagram picture contests and six Instagram caption contests were held per semester, and five YouTube/Instagram video contests. Additionally, an essay (first person "reporter" story) contest and a pledge contest (members and any currently enrolled student could pledge on behalf of a specific RIO to become a DOD on next license renewal). In addition, two random drawings were held: one in the first week of classes at a campus center table, and another at the end of a semester for contest entrants who entered but did not win a contest. Finally, a referral program was created where those who won a contest more than two times in one semester (and, thus, were no longer eligible to enter that semester) could win a prize by referring another student to enter a contest if that student subsequently won. There were nine themes for the Instagram picture/caption contests, and five themes for Instagram/YouTube (15-60 seconds) video contests.

Table 1 (see next page) lists the specific intervention protocols / themes for each contest on a social media site.

Table1: Organ donation related themes for Social Media contests			
Theme	Instagram picture contest	Instagram Caption contest	YouTube video contest
Hug a Heart!	Sp2015 Fa2015 Sp2016 Fa2016	Sp2015 Fa2015 Sp2016 Fa2016	
Go green recycle yourself!	Sp2016	Sp2016	Sp2015 Fa2015 Fa2016
Be a SUPER HERO! Organ donors can save 8-20 people	Sp2015 Fa2015 Fa2016	Sp2015 Fa2015 Fa2016	Sp2015 Sp2016
What are the odds? You're more likely to need an organ transplant than to be a donor when you die	Sp2015 Sp2016	Sp2015 Sp2016	Sp2015 Fa2015 Fa2016
Bust a myth! Find a myth about organ donation and expose the truth	Sp2015 Fa2015 Fa2016	Sp2015 Fa2015 Fa2016	Sp2015 Sp2016
Not as many as you think! Only 20% of Hawaii college students are designated organ donors	Sp2015 Fa2015 Fa2016	Sp2015 Fa2015 Fa2016	
I'm gonna tell MOM! Talk to your mom (and other family) about your wishes to be a donor	Sp2015 Fa2015 Sp2016 Fa2016	Sp2015 Fa2015 Sp2016 Fa2016	Sp2015
This is what a donor looks like	Sp2015		

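### The primary pre/post t-test makes no adjustment for calendar time, so a trend that continues after the start is counted as intervention effect; a supplementary time-adjusted estimate would be a cheap improvement

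*Combined protocol and SAP*

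**What the plan says.** The study design section describes "a sequential, multiple baseline survey design that was introduced over two years at the three Hawaii university campuses", with three intervention semesters at UHM and two each at UHH and HPU. The social media contest section places the largest number of contests as "held in the Spring of 2016 when all three sites were active in the intervention".

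Under 4) Statistical Analyses Protocols, the primary cross-sectional model is logistic, with one indicator for each of the 20 school-by-time assessments and adjustment for age, sex, race and religion. Then "the predicted statuses were compared between pre-intervention and post-intervention assessments using a t-test to test the primary hypothesis". For subgroups: "We also repeated the test within subgroups defined by school and by covariates". The models are repeated in the longitudinal sample and within low and high propensity strata.

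The power section simulates "comparing the 9 pre- and 11 post- intervention assessments, using our analysis approach". It reports that the minimum detectable difference (MDD) "was 4 percentage points for an average change overall (3 campuses) and was 7 percentage points within a single campus", and adds: "this was true assuming no change or a 3 percentage point drift in the pre-intervention prevalences over time".

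**The concern.** The 20 indicators let every campus and date have its own prevalence, but they do not adjust the contrast built from them, which only sets the pre predictions against the post predictions. Post assessments fall later than pre assessments. Any common movement in donor status that continues through the study, for reasons unrelated to the contests, is therefore added to the estimate.

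A multiple baseline design offers a way to separate the two, because at some dates one campus has started and another has not. No stated analysis makes that comparison. The stagger only dilutes a common trend, by placing some pre assessments at the later campuses on dates when UHM is already post.

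The other analyses do not remove a trend. The by-school test is the same contrast within one campus. The longitudinal models repeat it, and the test of adoption against zero among prior non-donors has no concurrent comparison. Propensity strata each carry the same trend. At stake is whether a pre/post change can be described as an intervention effect.

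**Working it through.** **Inputs from the power section:** 240 surveys per assessment, 60% baseline prevalence, 9 pre and 11 post assessments, two-sided 5% level, 80% power. The covariates and repeat respondents are ignored here.

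**1. The plan's own figure.**
- SE = sqrt[(0.60 × 0.40 / 240) × (1/9 + 1/11)] = sqrt(0.001 × 0.2020) = 1.42 points.
- Significance threshold: 1.96 × 1.42 = 2.79 points.
- MDD: 2.80 × 1.42 = 3.98 points, against the stated 4.
- Single campus, with the split assumed in step 2: 2.80 × sqrt[0.001 × (1/2 + 1/5)] = 7.4 points for UHM, and likewise 7.2 for UHH (3/3) and 6.8 for HPU (4/3), against the stated 7.

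A check with reported counts uses the 2,129 pre-intervention surveys of the propensity model (assumed to be all of them), 4,837 − 2,129 = 2,708 post surveys, and p = 1,137/2,129 = 0.534. It gives SE 1.44, threshold 2.83 and MDD 4.05.

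**2. How much trend passes through (assumed layout).** Count months from November 2014 and treat the survey at the start of a campus's first intervention semester as pre. One layout that fits the stated 9/11 split is:
- UHM: pre 0, 2.5; post 6, 9.5, 13, 14.5, 18.
- UHH: pre 0, 6, 9.5; post 13, 14.5, 18.
- HPU: pre 0, 6, 13, 14.5; post 18, 21.5, 24.5.

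The mean pre date is 51.5/9 = 5.72 months and the mean post date 170.5/11 = 15.50. The gap is 9.78 months out of 24.5, so a share of 0.40 of a linear whole-study trend enters the pooled estimate. Within campus the gaps are 10.95, 10.0 and 12.96 months. Their average is 11.3, a share of 0.46.

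**3. False positives with no intervention effect.** For bias b, the rate is Φ(b/SE − 1.96) + Φ(−b/SE − 1.96).

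| Rise over whole study | Spurious effect (0.40 × rise) | False positives |
|---|---|---|
| 0 | 0 | 5% |
| 1 point | 0.4 | 6% |
| 2 points | 0.8 | 9% |
| 3 points | 1.2 | 13% |
| 5 points | 2.0 | 29% |

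For trend alone to bring the expected estimate to the threshold, the rise must be 2.79/0.399 = 7.0 points. To mimic a 4-point effect it must be 4/0.399 = 10.0 points. A 3-point fall cuts power for a true 4-point effect from 80% to about 50%.

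Across other inferred layouts, pooled and within-campus contrasts, and a normal test or a t-test on the 20 values, a 3-point rise gives about +1.0 to +1.6 points and 11-20% false positives.

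**4. The drift sentence.** If the 3-point drift ran over the whole study, the added effect needed for 80% power in the unadjusted contrast would be 3.98 − 1.20 = 2.8 points (rise) or 3.98 + 1.20 = 5.2 points (fall). Neither is 4. The sentence gives no direction, no behaviour after the start and no type I error, so what was simulated is unclear.

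**5. A time-adjusted model.** Take campus effects, calendar time and a post-intervention indicator. With w the least-squares weights of the post term, SE = sqrt(0.001 × Σw²). On the layout above, linear time gives SE 2.51 and MDD 7.0 points; semester effects give 2.28 and 6.4. Across inferred layouts the MDD is about 6.4-9.7 points, and power for 4 points about 20-42%. Under a linear 3-point rise, linear time leaves no bias and semester effects about 0.3 points on this layout.

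If the true effect instead grows in proportion to time since the start and averages 4 points over the 11 post assessments, the same weights return 1.5 points (linear) and 2.0 (semester) here, and about 0.3-2.2 across layouts.

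**The case against.** The strongest reply is that the remedy has faults of its own, and most of that stands. The adjusted model assumes an immediate, constant effect, whereas the contests ran for two or three semesters and an effect could accumulate. The recruitment section describes the website as open-access, and contest posts were public, so campuses that had not started are not clean controls. Power is low.

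A second reply is that averaging pre/post differences within campus would answer the concern, and that the overall figure for three campuses may already mean this. It removes differences in campus mix, but it passes slightly more trend into the estimate (0.46 against 0.40 above) and raises the MDD to about 4.1-4.7 points. It is not a remedy for trend.

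A third reply is that time and study site were both offered to the stepwise propensity model on pre-intervention surveys and neither was retained. This is weak evidence against a large trend or campus gap. With 2,129 surveys, power was only about 6-23% for a 3-point drift and about 31-48% for a 5-point campus gap. It is also not an adjustment of the primary test.

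A reader might infer that the 4-point MDD proves that no time adjustment was used, or that the stagger is ignored altogether. Neither is supported. The figure matches an unadjusted contrast only without drift, and the pooled contrast benefits in part from the stagger.

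**Conclusion.** The point holds as a cheap improvement. As written, the primary test counts a trend that continues after the start as intervention effect, and no other stated analysis removes it. That follows whenever post assessments are later on average than pre assessments.

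The size does depend on assumptions: an inferred calendar, a linear common trend and independent surveys. On these, a 3-point whole-study rise takes the false-positive rate from 5% to roughly 11-20%. A reader might go further and infer that an observed pre/post change was trend. The documents do not support this. They report no trend, a 3-point rise would usually not reach significance, and on the layout worked above a 4-point artefact would need a rise of about 10 points.

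**What to change.** 1. Keep the primary test unchanged. Report the 20 predictions by campus and date with confidence intervals, so that a reader can look for movement before the start.
2. Add a supplementary analysis with campus effects, calendar time (linear or semester), a post-intervention indicator and the same covariates. Report its risk difference and confidence interval beside the primary result. Label it as specified afterwards (the surveys ended in December 2016 and the document is dated May 2023), and do not use it as a pass/fail gate. State its limits: the low power, the assumption of an immediate constant effect, and possible contamination through the open website and public posts. Say plainly that a null adjusted result does not show that the change was trend.
3. Word the conclusion as a pre/post change to the extent that a trend cannot be excluded.
4. Restate the drift sentence in the power section with the scenario simulated (direction, and behaviour after the start) and the type I error when drift continues.
5. Leave out within-campus reweighting, or report it only as a sensitivity analysis for campus mix, noting the larger share of trend and the higher MDD.

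The cost is wording, a re-run on data already held and a repeat of the drift simulation. The main risk is over-reading an imprecise adjusted estimate, which the labelling in item 2 is meant to prevent.
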